### **7.4 Test Article(s) (Study Drug(s) and/or Study Device(s))**

#### **7.4.1 Description**

The study drugs to be compared are Propofol (trade name: Diprivan; produced by Fresenius Kabi,USA; concentration 10mg/mL) and Methohexitol (produced by PharMEDiUM; concentration 10mg/mL). Given several current drug shortages, prefilled methohexitol syringes may not always be available from the pharmacy, in which case methohexitol may have to be mixed by hand by the attending anesthesiologist. Safety precautions have been described to ensure that the

correct concentration and dose have been prepared (see section 7.4.6.3. Both propofol and methohexitol are FDA approved anesthetic agents and considered standard of care. Drug inserts are provided in CATS IRB.

#### **7.4.2 Treatment Regimen**

Propofol: anesthesia will be induced using up to 2.5mg/kg of intravenous propofol administered in the manner described above (Section 7.2.2). If no loss of eye lash reflex results following this dose, an additional 0.5mg/kg of propofol will be administered in the manner described above (Section 7.2.2).

Methohexitol: anesthesia will be induced using up to 1.5mg/kg of intravenous methohexitol administered in the manner described above (Section 7.2.2). If the eye lash reflex is not lost after 1.5mg/kg of methohexitol, an addition 0.5mg/kg of methohexitol will be administered in the manner described above (Section 7.2.2).

#### **7.4.3 Method for Assigning Subject to Treatment Groups**

The randomization scheme for this study will use variable-size, random permuted blocks to ensure that the number of participants in each treatment arm is balanced after each set of  $B$  randomized participants, where  $B$  is the block size. We will use a block size of 10. Furthermore, the randomization will be stratified by gender (male/female) and drug type (ACEI/ARB). Randomization to the propofol or methohexitol arms will use 1:1 allocation. A research coordinator will access the randomization lists (developed through the website Randomization.com) stored in the secure REDCap database to randomize the participant.

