## **4.0 Recruitment Methods**

### **4.1 Identification of subjects**

The list of patients to present to the Anesthesia Preoperative Clinic will be reviewed on a daily basis by a provider or research associate who is directly involved in this study. All ASA Physical Class II or III patients undergoing elective surgery under general anesthesia will be identified as potential study participants. Their electronic medical record (EMR) will be reviewed by one of the study physicians in order to see whether they meet the inclusion or exclusion criteria. If they are eligible for the study, a member of the study team will approach them during their Preoperative Clinic visit, to ask them whether they would be willing to participate in this study.

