## **5.0 Consent Process and Documentation**

### **5.1 Consent Process**

#### **5.1.1 Obtaining Informed Consent**

##### **5.1.1.1 Timing and Location of Consent**

Consent will be personally obtained by the attending anesthesiologist in the same day unit prior to their surgery.

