#### **7.2.2 Day of surgery**

Randomization: The anesthesiologist assigned to administer anesthesia to the study patient will confirm the patient's study consent and ensure that the patient is still willing to participate in the study. A randomization protocol will have been created using randomization.com to randomly assign 106 patients to either the Propofol or Methohexitol groups. After the attending anesthesiologist ascertains that the patient will participate in the study, the randomization protocol will be used by a research technologist to assign the subject to a study group. The research technologist will then inform the attending anesthesiologist of which treatment the patient should receive (propofol or methohexitol).

Baseline Blood Sample Collection: Patients will not receive any premedication in the preoperative area. If they experience severe anxiety, they will be given premedication although this will exclude them from study participation. Intravenous access will be established in the preoperative area by the staff anesthesiologist using 1% lidocaine for local anesthesia if the patient requests it. This IV will be used to draw blood samples preoperatively as well as intraoperatively and to administer intravenous medications and fluids intraoperatively according to current anesthetic standards of care. An appropriately-sized blood pressure cuff will then be

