#### **7.4.5 Blinding of the Test Article**

The test drug will not be blinded

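### Staff assign treatment from stored randomization lists in an open-label, single-site trial, and nothing in the plan hides later assignments from them or keeps them out of recruitment

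*Combined protocol and SAP*

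**What the plan says.** Section 7.4.3 (Method for Assigning Subject to Treatment Groups) describes 1:1 permuted-block randomization, stratified by gender and by ACEI or ARB. It then says: "A research coordinator will access the randomization lists (developed through the website Randomization.com) stored in the secure REDCap database to randomize the participant". The same section calls the blocks variable in size and also states "We will use a block size of 10".

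Section 7.2.2 (Day of surgery) names a different role: "the randomization protocol will be used by a research technologist to assign the subject to a study group". It also fixes the order of events. Assignment comes "After the attending anesthesiologist ascertains that the patient will participate in the study", and afterwards "The research technologist will then inform the attending anesthesiologist of which treatment the patient should receive".

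Three other sections matter:

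- Section 5.1.1.1: "Consent will be personally obtained by the attending anesthesiologist in the same day unit prior to their surgery".
- Section 4.1, on first contact with eligible patients: "a member of the study team will approach them during their Preoperative Clinic visit".
- Section 7.4.5: "The test drug will not be blinded".

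Section 18.0 marks multi-site research as not applicable, and section 7.2.1 limits treatment of study patients to three trained anesthesiologists.

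**The concern.** Concealment of the next assignment is what keeps the choice of patients independent of treatment. In an open-label trial run by a small team at one site it carries more weight than usual, because past assignments are common knowledge and nothing later in the trial masks the arm.

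The plan says who opens the lists and where they are stored. It does not say what a list user can see. Secure storage protects the lists from outsiders, not from the people authorized to use them. If a user can look past the current line, the next assignments in that stratum are known before the next patient in it is confirmed. Both stratification factors are available when the record is screened.

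Several decisions leave room for judgement: whom to approach, whether coronary disease counts as severe, and whether intravenous access is suspected to be difficult (section 3.2). If any of these came to depend on the expected arm, the groups would differ in ways that adjustment for gender and inhibitor type does not remove. The intent-to-treat rule in section 8.3 starts at randomization and cannot correct selection before it. Under section 5.1.2, no identifiable information is kept on patients judged unsuitable, so such a pattern would be hard to detect afterwards.

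**Working it through.** **1. The plan's own sample size.** This is context only; concealment does not change it. Section 8.1 gives 47 per arm for 90% power, a difference of 0.30 and a two-sided 5% chi-square test. Section 8.2 expects a propofol rate slightly above 0.82 without giving a figure, so 0.85 against 0.55 is an assumption. The mean rate is 0.70, and

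n = [1.960·√(2·0.70·0.30) + 1.282·√(0.85·0.15 + 0.55·0.45)]² / 0.30² = 46.9, rounded up to 47.

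Allowing for 20% drop-out, 94/0.80 = 117.5, rounded up to 118, against 120 stated. The plan's figures reproduce, and 0.85 is a reasonable working rate.

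**2. Safeguards looked for in the text.**

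| Safeguard | In the plan? |
|---|---|
| Assignment after participation is confirmed | Yes, 7.2.2 |
| Consenting clinician differs from the assigner | Yes, 5.1.1.1 with 7.2.2 |
| Clinician learns the arm only after assignment | Yes, 7.2.2 |
| One assignment released at a time | Not described |
| Later entries hidden from the list user | Not described |
| List users kept out of screening and approach | Not described; 4.1 allows any study team member |
| One named role for the task | No: technologist in 7.2.2, coordinator in 7.4.3 |

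The three safeguards present protect the current patient's assignment, provided the list was not seen earlier. None of them covers the next patient in the same stratum.

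**3. How much could be known.** If entries can be viewed, every later assignment in the stratum is known. For comparison, suppose the lists are hidden but the block size of 10 is known and past assignments in the stratum are tracked. An assignment is certain once only one arm remains in the block. The chance that the last k assignments are all the same is 2·C(10−k, 5)/C(10, 5). Summing over k = 1 to 5 gives

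(252 + 112 + 42 + 12 + 2)/252 = 420/252 = 1.67 of every 10 assignments.

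The best guess would be right 65.3% of the time, against 50% by chance. This second route does not depend on list access and is a separate weakness.

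**4. Illustration of the effect on the test.** Take 60 per arm and two drugs with the same true effect. Suppose selection lowers one arm's underlying risk by 5% or 10% relative. The rejection rate is the sum of the two binomial probabilities over all outcome pairs for which the uncorrected two-sided chi-square test rejects at 5%. Because the base rate is assumed, a range is shown.

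| Base rate | No selection | 5% lower | 10% lower |
|---|---|---|---|
| 0.82 | 4.8% | 8.6% (0.779) | 19.4% (0.738) |
| 0.85 | 4.7% | 9.0% (0.8075) | 21.6% (0.765) |
| 0.88 | 4.9% | 10.0% (0.836) | 24.7% (0.792) |

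The planned primary analysis is a log-binomial model adjusted for the two stratification factors, so these figures show scale rather than the exact operating characteristics.

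**The case against.** The strongest reply is that the plan never says the lists are displayed in full. A reader might infer from the wording on accessing the lists that the whole sequence is open and upcoming assignments are visible. The documents do not support that as fact. The same wording fits lists loaded into REDCap and released one line at a time. What stands is narrower: the plan does not say which of the two applies, and nothing in it rules out the first.

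A second reply is that roles are already separated. The anesthesiologist who takes consent is not the person who assigns, and learns the arm only afterwards. This is right, and no section gives that clinician access to the lists. It does not cover the technologist or coordinator, who is not barred from screening or approaching patients.

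A third reply concerns timing. Patients are approached at the clinic visit, but list position is set by the order of confirmations on the day of surgery within four strata. Someone in clinic would have to predict that order to use the list. This weakens the route through clinic approach. It does not close the route on the day of surgery, when the next assignment in a stratum could be known before consent is settled.

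Finally, the 5% and 10% shifts come from nowhere in the plan, and no mechanism is shown that would produce them. That is accepted; they indicate scale only.

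**Conclusion.** The point holds as a gap in allocation concealment. Staff work from stored lists, two sections name different roles for the task, and nothing hides later assignments from list users or separates them from recruitment. The order of consent and assignment reduces the exposure without removing it.

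The documents do not show that anyone can see future assignments, that the consenting anesthesiologist has list access, or that selection would occur. The possible bias therefore cannot be estimated. The rates of about 9% and 22% rest on an assumed propofol risk of 0.85, 60 analysed per arm, an unadjusted test and assumed selection effects of 5% and 10%; they are not forecasts.

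The change should be made because it protects the primary comparison at little cost. If one-at-a-time release is already intended, a sentence saying so, together with the access restriction and a single named role, resolves the point.

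**What to change.** In section 7.4.3, replace access to the lists with release of a single assignment through REDCap, available only after eligibility and consent have been recorded for that patient. State that no one who screens, approaches, consents or treats patients can view the lists. Name the same role for the task in 7.2.2 and 7.4.3.

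While editing 7.4.3, reconcile the variable block sizes with the single size of 10, and keep the sizes used from recruiting and treating staff. Hiding the lists does not remove the predictability of a known fixed block.

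The cost is a small REDCap set-up step in a system that already holds the lists. Section 5.1.2 mentions limited research personnel, so the team should check that someone outside recruitment and treatment can load and hold the lists. Sample size and patient care are unaffected.

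The change does not deal with removals once the arm is known, such as those for non-adherence in sections 3.3.1 and 7.2.2. These remain possible under perfect concealment and depend on whether outcomes are still collected for the intent-to-treat analysis.

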#### **7.4.4 Subject Compliance Monitoring**

Not applicable

#### **7.4.5 Blinding of the Test Article**

The test drug will not be blinded

#### **7.4.6 Receiving, Storage, Dispensing and Return**

##### **7.4.6.1 Receipt of Test Article**

The study drug will be obtained from the pharmacy-stocked Pyxis machines in each operating room or from the dedicated operating room pharmacy, which is standard of care.

##### **7.4.6.2 Storage**

Not applicable

##### **7.4.6.3 Preparation and Dispensing**

Refer to Anesthesia Protocol Sheet for Anesthesiologist for specific instructions on preparation and administration of study drugs. The study drugs will be prepared by one of the study anesthesiologists, and preparation and dose to be administered will subsequently be verified by another study anesthesiologist or

a study CRNA (if they are clinically available). Documentation of training by the checking anesthesiologist or certified registered nurse anesthetist (CRNA) will be required. The study team will provide a copy of the protocol and prepare a training document that summarizes the study and the checking anesthesiologist (or CRNA) responsibilities. A delegation log will be maintained to document this training. Only trained providers may act as the checking anesthesiologist for the research.

Anesthesia induction will be performed by one of the trained co-investigator anesthesiologists as described above.

The exact dose of propofol to be used for induction will be divided into two doses of identical volume, each half-dose placed in a sterile 60ml syringe by the administering anesthesiologist. The exact dose of methohexitol to be used for induction will be divided into two doses of identical volume, each half-dose placed in a sterile 60ml syringe by the administering anesthesiologist. This division of doses and placement into 60ml syringes is required to attain the infusion rate required by our study protocol by using the Medfusion 3500 pumps available at our institution. Both drugs will be administered via pre-established intravenous access by using Medfusion 3500 pumps at a pre-programmed rate of infusion during anesthetic induction.

#### **7.4.6.4      Return or Destruction of the Test Article**

Residual propofol wastage is not routinely documented. Remaining drug is discarded into operating room waste containers.

Residual methohexitol wastage will be handled according to protocols determined by our drug pharmacy whenever this drug is used for anesthesia induction. This includes recording the exact amount of methohexitol utilized (both on the EMR and on paper) and returning all remaining methohexitol to the pharmacy at the termination of surgery.

#### **7.4.6.5      Prior and Concomitant Therapy**

Not applicable.

### **8.0      Subject Numbers and Statistical Plan**

#### **8.1      Number of Subjects**

The total sample size will consist of 120 participants (i.e., 60 per treatment arm). A sample size of 47 subjects per group will provide 90% statistical power to detect a difference of 0.3, between the proportion of subjects having at least one hypotension episode in the propofol group compared to the proportion in the methohexitol group, using a two-sided, chi-square test having a significance level of 0.05. However, we anticipate a drop-out rate as high as 20% for this study; therefore, we will enroll a total of 120 subjects.

## 8.2 Sample size determination

The primary outcome of this two-arm trial is the proportion of subjects that have at least one hypotension episode within 15 minutes of administration of the randomized treatment medication. A hypotension episode is defined as having a drop in systolic blood pressure  $>30\%$  from baseline and/or having systolic blood pressure  $<85$  mmHg. Eyraud et al found 42 out of 51 subjects (0.82) had at least one hypotension episode using propofol (Eyraud et al., 1999). We expect our propofol proportion to be slightly higher due to our definition of a hypotension episode and our patient population. Further, we believe an absolute reduction of 0.30 in the proportion of subjects having at least one hypotension episode in the methohexitol group compared to the propofol group is clinically important. Although the randomization will be stratified by two factors (gender and drug type), to provide a conservative sample size estimate these factors were not taken into consideration for the power analysis because the correlation of these stratification covariates with the outcome would simply increase the precision, and hence, increase the power.

## 8.3 Statistical methods

Primary analyses will invoke an intent-to-treat paradigm, wherein all randomized subjects are included according to their randomized treatment arm, regardless of actual treatment received, compliance, etc. Data will be summarized using descriptive statistics for continuous variables (mean, standard deviation, number of observations, and percentiles) and frequency statistics (frequencies and percentages) for categorical variables. Univariate and bivariate distributions will be inspected in order to address any missing data, inconsistent responses, outliers, and data entry errors. The sample size estimates have taken into consideration a participant drop-out of 20%; however, every effort will be made during the studies to minimize any drop-out. All hypothesis tests will be two-sided and analyses will account for the two randomization stratification factors of gender and inhibitor type. All analyses will be performed using SAS software, version 9.4 (SAS Institute, Inc., Cary, NC), R software, version 3.2.2 (R Foundation for Statistical Computing, Vienna, Austria), or Stata software, version 13 (StataCorp LP, College Station, TX).

For the primary outcome of the proportion of participants having at least one hypotension episode, log-binomial regression will be used to compare the propofol and methohexitol groups, adjusting for the randomization stratification factors of gender and inhibitor type. Because this is a prospective study, the log-binomial model allows us to estimate the risk ratio rather than the odds ratio while adjusting for covariates (Wacholder, 1986).

For secondary outcome of the proportion of patients experiencing refractory hypotension, the log-binomial model as described for the primary outcome will be used to compare the treatment groups. Poisson regression will be used to compare the two treatment groups, adjusting for the randomization stratification factors, with respect to the secondary outcomes of (a) the number of vasopressor doses (i.e., ephedrine, phenylephrine and vasopressin) administered per patient and (b) the number of hypotension episodes per patient over the first 18 after treatment initiation. In the event that there is an excess of zero counts, zero-inflated Poisson (ZIP) regression will be considered (Lambert, 1992).

For secondary hemodynamic outcomes of systolic blood pressure, diastolic blood pressure and heart rate over the first 15 minutes after treatment initiation, the area under the curve (AUC) for each of these variables will be calculated using the trapezoidal rule. The AUC of each of these variables will be compared between the two treatment groups using linear regression models adjusting for the randomization stratification factors. A linear regression model also will be used to assess differences between the two treatment groups with respect to the duration (in minutes) of hypotension.

Blood will be collected at baseline, 3 min, 5 min, 10 min, and 15 min after treatment initiation to assess changes from baseline in AVP, AI, Epi and NE between the two treatment groups. For these continuous secondary outcomes collected longitudinally, linear mixed-effects models will be fit to compare the two treatment arms with respect to changes in these outcomes over time(Laird and Ware, 1982). The independent variables in the model will be treatment arm, time, the interaction of treatment and time, as well as the randomization stratification factors as covariates. From the mixed-effects models, contrasts will be constructed to test the hypotheses of interest with respect to changes over time in the outcomes. Linear mixed-effects models are an extension of ordinary regression models that account for the between- and within-subject correlation inherent in data involving repeated measurements per subject and allows for the variance-covariance matrix to be explicitly defined.

Following our assessment of the initial fit of the models, we will add covariates to the models that correspond to potential confounders to assess their impact, if any, on the treatment effects. Residual diagnostics will be assessed to determine the appropriateness of the model fit and, if necessary, transformations of the response will be used to meet modeling assumptions. Differences in means and associated confidence intervals (CIs) will be used to quantify the magnitude of the effects for continuous outcomes.

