applied to the ipsilateral arm. An appropriately-sized blood pressure cuff shall be defined as a cuff whose bladder length is at least 80% of the arm circumference, and whose width covers 2/3 of the distance from the elbow to the shoulder. Blood samples, for baseline analysis of AVP, All, NE and Epi levels, will be collected from the IV as follows: A tourniquet will be applied proximal to the intravenous catheter, following which 3cc of blood will be removed first to clear the 'dead space' in the intravenous line and prevent erroneous blood sampling. This blood will be discarded. A further 10cc of blood will be collected in appropriately labeled tubes (5ml in serum red top vacutainers tubes and 5ml in vacutainers tubes containing EDTA) and kept on ice until processing by our research technician, as described below. Following collection of the blood sample, 5cc of normal saline will be used to flush the line and prevent blood from clotting the catheter. A second IV will also be established in the preoperative area under local anesthesia as described above to administer intravenous medications and fluids intraoperatively according to current anesthetic standards of care.

**Operating Room Procedures:** Subjects will be attached to standard ASA monitors including electrocardiogram and pulse oximetry and noninvasive blood pressure monitor. Baseline blood pressure will be determined by taking three automated successive non-invasive blood pressure measurements every 1-2 minutes, until the systolic blood pressure (SBP) measurements is consistent (difference of no more than 10% between readings) with the patient lying in supine position. The average SBP and accompanying heart rate (HR) of these three measurements will be recorded as mean baseline values.

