### **10.2 Data that are reviewed**

Both propofol and methohexitol have a long record of safety in anesthesia practice. However, the investigators will monitor for new safety and adverse data of these drugs as presented by medical literature to ensure that our subjects remain safe throughout the conduct of this study. Our interim analysis, as described above, will be performed using hemodynamic data (blood pressure, heart rate) and vasopressor type and dosage, as obtained from the RedCap database.

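### The only primary model, an adjusted log-binomial regression, ends on its boundary in about 16–26% of trials at the planned 120 patients, and no alternative is pre-specified

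*Combined protocol and SAP*

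**What the plan says.** Section 8.3 gives one model for the primary outcome, whether a patient becomes hypotensive at all: "log-binomial regression will be used to compare the propofol and methohexitol groups, adjusting for the randomization stratification factors of gender and inhibitor type". It is chosen because it yields a risk ratio. The analysis is by intention to treat, with "all randomized subjects are included according to their randomized treatment arm", so 60 per arm is the planned analysis size.

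Section 8.3 has two provisions for model trouble, and neither applies here. Zero-inflated Poisson is reserved for count outcomes, and transforming the response cannot help a yes/no outcome. Nothing says what happens if the log-binomial fit does not converge or gives a fitted risk of 1. The chi-square test appears only in section 8.1, as the basis for the sample size.

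On the expected risk, section 8.2 cites an earlier study with 42 of 51 propofol patients hypotensive (0.82) and adds: "We expect our propofol proportion to be slightly higher due to our definition of a hypotension episode and our patient population". Section 8.1 states: "A sample size of 47 subjects per group will provide 90% statistical power to detect a difference of 0.3".

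On who could see what, section 7.4.5 says "The test drug will not be blinded", and section 10.2 says "Our interim analysis, as described above, will be performed using hemodynamic data (blood pressure, heart rate) and vasopressor type and dosage". Section 10.1 schedules this after every 30 patients.

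**The concern.** The model is log(risk) = intercept + arm + gender + inhibitor type, and this sum may not exceed 0. When the true risk is high and the strata are small, it is quite likely that every propofol patient in some stratum has an event. The maximum-likelihood fit is then often pushed to a fitted risk of exactly 1. A constrained estimate still exists there, but the usual standard error and Wald interval no longer hold, and standard software may stop with an error.

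Someone must then choose another analysis of the primary endpoint with the data and treatment assignments in view. What is at stake is the false-positive rate of the main comparison and the claim that the primary analysis was fixed in advance.

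**Working it through.** **1. The plan's own figure.** Inputs from sections 8.1 and 8.2: difference 0.30, two-sided 0.05, power 90%, chi-square test. With pooled variance,

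n = {1.960·√[2p̄(1−p̄)] + 1.2816·√[p₁(1−p₁) + p₂(1−p₂)]}² / 0.30².

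- 0.85 versus 0.55: (1.960 × 0.6481 + 1.2816 × 0.6124)² / 0.09 = (1.2702 + 0.7848)² / 0.09 = 46.9, so **47**.
- 0.82 versus 0.52: 49.5, so 50. Propofol risks of 0.84 and 0.86 give 48 and 46.

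The printed 47 is reproduced, and it points to a propofol risk of 0.85. That value is not printed, so 0.82 to 0.85 is used as the range. Dropout: 94/0.80 = 117.5, consistent with 120.

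**2. Chance that a propofol stratum has events in every patient.** With equal strata there are 60/4 = 15 patients in each of four strata.

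- At 0.82: 1 − (1 − 0.82¹⁵)⁴ = 1 − (1 − 0.051)⁴ = 19%.
- At 0.85: 1 − (1 − 0.087)⁴ = 31%.

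Such a stratum does not always force the additive model to its limit, so the boundary share needs simulation.

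**3. Share of trials with the fit on the boundary.** The log-binomial likelihood was maximised subject to fitted risks of at most 1, using several separately coded fits and 1,500 to 10,000 trials per scenario. Ranges show the spread across runs. Stratum sizes and covariate effects are assumptions, because the documents give none.

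| Scenario | 0.82 vs 0.52 | 0.85 vs 0.55 |
|---|---|---|
| 60 per arm, equal strata, no covariate effect | 15.5–16.5% | 25.9–26.5% |
| 60 per arm, unequal strata | 18–19% | 26–27% |
| 60 per arm, both covariates with risk ratio 1.1 | 26–27% | 43% |
| 47–48 per arm (20% dropout), equal strata | 26–29% | 38–39% |
| 60 per arm, both arms at the propofol risk | 14–16% | 24–25% |

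A boundary fit is not the same as software failure, which depends on the program. One iteratively reweighted fitter failed in 9–15% of trials at 60 per arm.

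**4. Type I error with no treatment difference, 60 per arm** (Monte Carlo error about 0.5 point).

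| Analysis | Both arms 0.82 | Both arms 0.85 |
|---|---|---|
| Log-binomial Wald test, used even on the boundary | 9.2% | 10.6% |
| Wald, likelihood-ratio test on the boundary | 7.8–8.5% | 8.5–9.6% |
| Wald, robust Poisson on the boundary | 5.3–5.7% | 5.3–5.9% |
| Robust Poisson throughout (range over both rates) | 4.4–5.8% | 4.4–5.8% |

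The second row can be traced in one run. At 0.82, 15.66% of fits were on the boundary; there the likelihood-ratio test rejected in 32.5% and robust Poisson in 14.2%. Starting from 5.66% with the Poisson fallback: 0.0566 + 0.1566 × (0.325 − 0.142) = 8.5%. At 0.85: 0.0526 + 0.2376 × (0.250 − 0.112) = 8.5%.

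**5. Under the planned effect.** On boundary data at 60 per arm, the likelihood-ratio test and robust Poisson agreed on significance in 99% of trials. Their log risk ratios differed by 0.022–0.027 on average. Robust Poisson always gave an estimate; its power was 0.94–0.96 at 60 per arm and 0.88–0.91 at 47, within 0.01 of the likelihood-ratio test.

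**The case against.** The strongest reply is that the consequence is narrow. If methohexital reduces risk as planned, any sensible analysis reaches the same conclusion, and log-binomial regression is a legitimate way to estimate a risk ratio. The inflated error needs two things together: arms that do not differ, and an unfavourable choice on the boundary. An analyst who reached for robust Poisson would be close to 5%.

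Much of this stands as a limit on size:

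- The 16–26% belongs to the planned effect. Under no difference, where the choice matters, the share is about 14–25%.
- The upper end rests on the inferred 0.85.
- Not all of the likelihood-ratio excess comes from the boundary. With both arms at 0.70, where only 1.6% of fits are on the boundary, that test still rejects in 6.5%.
- The periodic reviews add little. Section 10.7 plans no statistical tests for monitoring, and the primary model would be fitted at the end. Open-label treatment is enough to make the point.

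It does not remove the concern. The unfavourable result needs no odd choice, since applying the named model with its usual Wald test regardless of the boundary gives 9.2–10.6%. That a statistician could handle this later is no answer, because later means after the unblinded data have been seen.

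**Conclusion.** The concern holds and should be fixed before analysis. At 60 per arm, the only primary model ends on its boundary in about 16% of trials at the printed propofol risk of 0.82, and in about 26% at the inferred 0.85. These figures assume equal strata and no effect of gender or inhibitor type. Unequal strata change them little; real covariate effects or dropout raise them. Depending on what is done then, the type I error lies between about 5% and 11%, and the plan does not say which course will be taken. Power and the expected conclusion under the planned effect are not threatened, and this point does not show the stated sample size to be wrong.

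**What to change.** Either of two changes to section 8.3 is enough:

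- Make Poisson regression with log link and robust (sandwich) variance, adjusted for gender and inhibitor type, the primary model.
- Keep log-binomial as primary and name that Poisson model as the fallback, used if the fit does not converge or if any fitted risk reaches 1. State a numerical tolerance for the latter, for example a fitted risk above 0.999. Fallback power at 60 per arm was 0.947 and 0.961 in the two planned scenarios.

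Both keep the risk ratio that section 8.3 wants. The cost is one or two sentences, with no change to the data or sample size and no material loss of power. The same wording can cover refractory hypotension, for which section 8.3 reuses the model.

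A separate improvement in the same section also costs nothing. The hemodynamic AUCs "will be compared between the two treatment groups using linear regression models adjusting for the randomization stratification factors", and further covariates are unnamed and come only after the initial fit. Section 7.2.2 already says: "The average SBP and accompanying heart rate (HR) of these three measurements will be recorded as mean baseline values". Naming baseline SBP and HR in advance as covariates in the matching SBP and HR AUC models would use data already collected. The gain in precision cannot be sized, because the documents give no correlations.
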